8. ADMINISTRATIVE MATTERS

The trial will be carried out in compliance with the protocol, the principles laid down in the Declaration of Helsinki, version as of 2013 in accordance with the ICH Harmonised Tripartite Guideline for Good Clinical Practice (GCP) and relevant SOPs.

The applicable international and local laws and treatment guidelines will be adhered to.

A no fault insurance cover will be provided and explained in the informed consent form.

8.1 ETHICS

8.1.1 Institutional Review Board or Independent Ethics Committee

The trial will not be initiated before the clinical trial protocol (CTP) and informed consent and

patient information form have been reviewed and received approval from the local Institutional Review Board (IRB)/Independent Ethics Committee (IEC) and approval by the Competent Authority (CA) or applicable regulatory authority as required by local laws and regulations. Should a CTP amendment be made that needs IRB/IEC approval and authority notification/approval, the changes in the CTP will not be instituted until the amendment and revised informed consent (if appropriate) have been reviewed and received approval / favourable opinion from the local IRB/IEC and the CA or applicable regulatory authority, as required by local laws and regulations. A CTP amendment intended to eliminate an apparent immediate hazard to patients may be implemented immediately providing that the regulatory authority and IRB / IEC are notified as soon as possible and an approval is requested. CTP amendments exclusively for logistical or administrative changes may be implemented with notification of the IRB / IEC and CA or competent authority only.

The constitution of the IRB/IEC must meet the requirements of the participating countries. A list of the IRB/IEC members, with names and qualifications, needs to be provided by the IRB/IEC to the investigator or, if applicable, sponsor.

8.1.2 Informed Consent and Patient Information

Prior to patient participation in the trial, written informed consent must be obtained from each patient (or the patient's legally accepted representative) or initial verbal and subsequent written consent according to the regulatory and legal requirements of the participating country. Each signature must be dated by each signatory and the informed consent and any additional patient information form retained by the investigator as part of the trial records. A signed copy of the informed consent and any additional patient information must be given to each patient or the patient's legally accepted representative.

The patient must be informed that his/her personal trial-related data will be used by the study sponsor in accordance with the local data protection law. The level of disclosure must also be explained to the patient.

The patient must be informed that his/her medical records may be examined by authorised monitors (CRA) or Clinical Quality Assurance auditors appointed by the sponsor, by appropriate IRB / IEC members, and by inspectors from regulatory authorities.

Should a CTP amendment become necessary, the patient consent form and patient information form may need to be revised to reflect the changes to the CTP. It is the responsibility of the investigator or, if applicable, sponsor to ensure that an amended consent form is reviewed and has received approval / favourable opinion from the IRB / IEC and CA or applicable regulatory authority, as required by local laws and regulations, and that it is signed by all patients subsequently entered in the trial and those currently in the trial, if affected by the amendment.

8.2 RECORDS

8.2.1 Drug accountability

The local investigator or pharmacist must maintain records of the delivery and use of medications for the study.

8.2.2 Case Report Forms (CRFs)

All of the clinical data will be captured via electronic data capture (EDC) using Open Clinica, a web-based application. The investigator site staff will enter and edit the data via a secure network, with secure access features (username, password and secure identification – an electronic password system). A complete electronic audit trail will be maintained. The investigator will approve the data using an electronic signature (Ref: 21 CFR Part 11), and this approval is used to confirm the accuracy of the data recorded.

Electronic CRFs (eCRFs) will be used for all patients. The investigator's data will be accessible from the investigator's site throughout the trial. Relevant medical history prior to enrolment will be documented at the baseline visit. The eCRFs must be kept current to reflect patient status at each phase during the course of the trial. The patients must not be identified on the eCRF by name. Appropriate coded identification (i.e. Patient Number) must be used. The investigator must make a separate confidential record of these details (patient identification code list) to permit identification of all patients enrolled in a clinical trial in case follow-up is required.

The investigator will be responsible for retaining all records pertaining to the trial as specified in the appropriate contract.

8.2.3 Source documents

According to ICH/GCP source documents provide evidence for the existence of the patient and substantiate the integrity of the data collected. Source documents are filed at the investigative site and will be verified to the eCRF by the CRA when indicated.

Data entered in the eCRFs that are transcribed from source documents must be consistent with the source documents or the discrepancies must be explained. The investigator may need to request previous medical records or transfer records. Current medical records must also be available.

8.2.4 Direct access to source data / documents

The investigator/institution will permit trial-related monitoring, audits, IRB/IEC review and regulatory inspection, providing direct access to all related source data / documents. ECRFs and all source documents, including progress notes and copies of laboratory and medical test results, must be available at all times for review by the sponsor's clinical trial monitor and inspection by health authorities. The on-site monitor may review all eCRFs, and written informed consents. The accuracy of the data will be verified by reviewing the source documents to the eCRF.

8.3 QUALITY ASSURANCE AUDIT

A quality assurance audit of this trial may be conducted by the sponsor or sponsor's designees. The quality assurance auditor will have access to all medical records, the investigator's trial-related files and correspondence, and the informed consent documentation that is relevant to this clinical trial.

8.4 PROCEDURES

8.4.1 Adverse events

An **adverse event (AE)** is defined as any untoward medical occurrence, including an exacerbation of a pre-existing condition, in a patient in a clinical investigation who received a pharmaceutical product. The event does not necessarily have to have a causal relationship with this treatment.

A **serious adverse event (SAE)** is defined as any AE which results in death, is immediately life-threatening, results in persistent or significant disability / incapacity, requires or prolongs patient hospitalisation, is a congenital anomaly / birth defect, or is to be deemed serious for any other reason representing a significant hazard, which is comparable to the aforementioned criteria.

Adverse events occurring during the course of the clinical trial (i.e. from signing the informed consent onwards through the observational phase) will be collected, documented and reported by the investigator according to the specific definitions and instructions detailed in the 'Adverse Event Reporting' section of the Investigator Site File and in section 5.2.1 of the trial protocol. Figure 2 in section 5.2.1 of the trial protocol shows an overview of the adverse event reporting.

Reporting of serious adverse events (SAE)s:

On an SAE form:

For the following events an **SAE form** (in addition to entering the SAE data in the eCRF) will need to be completed and emailed for expedited reporting:

- Serious and treatment-related SAEs
- Serious, not treatment-related and not mentioned on the 'list of STEMI-related events'

For each SAE, the investigator will provide the onset, end, treatment required, outcome, seriousness and action taken with the investigational drug. The investigator will also determine the relationship of the investigational drug to all SAEs.

The basis for judging the causal relationship between the investigational product and the SAE is described below.

Causal relationship*	
Yes	There is a reasonable causal relationship between the study drug administered and the AE.

No	There is no reasonable causal relationship between the study drug administered and the AE.
----	--

*Medical judgement should be used to determine the relationship, considering all relevant factors, including pattern of reaction, temporal relationship, de-challenge or re-challenge, confounding factors such as concomitant medication, concomitant diseases and relevant history.

These completed SAE forms need to be emailed within 24 hours (1 workday) after the Investigator (or any member of the study team) has become aware of the event. Timelines are the same for initial reports and for follow-up reports.

Upon receipt of these SAE forms the treatment relationship, the category classification, listedness and seriousness of reported SAE cases will be assessed. Expedited reporting of serious adverse events, e.g. suspected unexpected serious adverse reactions (SUSARs), will be done according to local regulatory requirements within the required timelines.

In the eCRF:

Any SAE, whether or not considered related to the study medication, and whether or not the study medication has been administered, must be reported immediately in the eCRF.

Reporting of non-serious adverse events:

Non-serious events need to be recorded in the eCRF

8.5 RULES FOR AMENDING PROTOCOL

All CTP amendments must be documented, dated and signed by all signatories (or their successors) of the original protocol. This also applies to any local amendment that may become necessary. Amendments need to be submitted to the IRB / IEC for review/approval and to the competent authority (CA) or the applicable regulatory authority for approval/ notification, as described in section 8.1.1.

8.6 DISCONTINUATION OF THE TRIAL

The sponsor who initiated the study reserve the right to discontinue the trial at any time for the following reasons (please also refer to section 8.10):

- 1.) Failure to meet expected enrolment goals,
- 2.) Emergence of any efficacy/safety information that could significantly affect continuation of the trial or any other administrative reasons,
- 3.) Violation of GCP, the CTP, or the contract by a trial site or investigator, disturbing the appropriate conduct of the trial.

8.8 PUBLICATION POLICY

This study represents an investigator initiated effort supported by a pharmaceutical company and research foundations, and as such, the parties agree that the recommendation of the pharmaceutical company concerning manuscripts or text shall be taken into consideration in the preparation of final scientific documents for publication or presentation whenever these recommendations are related to their drugs.

The Executive Committee in conjunction with the Steering Committee will prepare a manuscript(s) plan to ensure timely and high quality presentation and publication of the study results and provide this also to the pharmaceutical company for due consideration.

Investigators are encouraged to propose additional analyses from the final available data. All proposed publications and presentations by investigators or their personnel and associates resulting from or relating to this study must be submitted to the Executive Committee in conjunction with the Steering Committee for review and approval prior to submission for publication or presentation. Manuscripts submitted for publication must be in compliance with applicable laws and regulations regarding patient privacy.

8.9 COMPLETION OF TRIAL

The IEC/competent authority in each participating EU member state and any other countries where notification is required needs to be notified about the end of the trial (last patient out) or early termination of the trial.

8.10 STUDY COMMITTEES

Data and Safety Monitoring Board

An independent Data and Safety Monitoring Board (DSMB) will monitor the accruing safety and outcome data.

The DSMB will be composed of independent cardiologists including at least one interventional

cardiologist and one independent biostatistician.

The DSMB will review safety data. The DSMB will also conduct analyses of the data at the request of the Steering Committee and/or Executive Committee. The DSMB analyses and operations will be formally separated from the sponsor, pharmaceutical companies, the investigators and the Steering/Executive Committee. The DSMB will advise the executive committee- by giving recommendations on the trial continuation or aspects of the study conduct. After recruiting 50 % of the planned population a formal interim analysis will be performed by the DSMB to evaluate and advise the Executive Committee on the feasibility of increasing the sample size in order to turn the study into a confirmatory trial. The tasks of the DSMB will be described in detail in the DSMB charter.

Stroke Review Panel

An independent Stroke Review Panel will perform a final evaluation and classification of documented clinically suspected strokes.

The Stroke Review Panel members will include an independent neurologist and a neuroradiologist. All the clinically suspected stroke events will be reviewed by the Stroke Review Panel blinded to the allocated treatment. On the basis of the stroke event documentation the Stroke Review Panel will assess and classify each stroke event as primary haemorrhagic or ischaemic or unclassifiable.

The classification of the strokes will be made available for the periodical DSMB reviews.

Executive Committee

The Executive Committee is composed of [name] (co-chair), [name] (co-chair), [name] (co-PI), [name] (co-PI), [name]. It provides scientific direction of the study and assesses the study progress. The Executive Committee is assisted by the Steering Committee. The Executive Committee Chairmen are responsible for communicating with the DSMB when appropriate.

The Executive Committee meets periodically by telephone or webcast.

Steering Committee

The Steering Committee is composed of the Executive Committee and members from all participating countries, usually the national coordinator(s) of every country. The Steering Committee meets periodically at the major international cardiology congresses to assess the progress, provide scientific input and address policy issues and operational aspects of the protocol. At the end of the trial the Steering Committee will meet in a closed session to discuss the trial results.

Operations Committee

The Operations Committee is responsible for all operational management issues in running the study on a daily basis. It is composed of members with operative responsibility for different areas like overall management, regulatory issues, monitoring, safety reporting, data management etc. It interacts closely with the Study Chairmen and the Executive Committee, the local clinical monitors and data management for the day-to-day conduct of the study.

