Dose and mode of administration	
Pre-hospital treatment:
 
In agreement with international guidelines, upfront antithrombin treatment, aspirin and a P2Y12 antagonist according to local standards and at the discretion of the investigator (e.g., unfractionated heparin/ enoxaparin or bivalirudin, clopidogrel or ticagrelor). Prasugrel is not recommended (cfr bleeding risk in elderly patients).
 
In-hospital treatment:
 
Maintenance dose of aspirin and a P2Y12 antagonist. Additional GP IIb/IIIa antagonists during PCI are at the investigator's discretion (eg for bail-out).

Criteria for efficacy	
Pharmaco-invasive strategy compared with primary PCI
 
Number of patients achieving $\geq 50\%$ ST-segment resolution before and after PCI in lead with maximal ST elevation at baseline; % rescue PCI; TIMI flow grades
 
Clinical events of interest i.e. death, shock, heart failure, recurrent MI, rescue PCI and aborted MI will be recorded and assessed as single or composite endpoints for evaluation.

Criteria for safety	
 - Total stroke, intracranial haemorrhage (ICH), ischaemic stroke, haemorrhagic conversion up to 30 days - Non-intracranial bleeds (total, major, minor, and blood transfusions) up to 30 days - Serious cardiac events (e.g. death, congestive heart failure, reinfarction, resuscitated ventricular fibrillation, repeat target vessel recanalization, stent thrombosis, total AV block etc) up to 30 days

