5.2.2 Specific safety recording within 30 days

Specific safety events to be recorded in this trial will be:

- Clinically suspected stroke (total (fatal, disabling, non-disabling); ischaemic; intracranial haemorrhage)

Patients experiencing any new neurological deficit at any time after randomisation (up to day 30) are to be taken for immediate (within 24 hours) computed tomography scanning (CT) or

magnetic resonance imaging (MRI) to determine whether a stroke or intracranial haemorrhage (ICH) has occurred. CT is preferred, but MRI is also acceptable. In addition, all patients concerned should also be seen by a neurologist who may assist with the completion of the necessary documentation.

If, in case of a fatal stroke and no imaging was done, an autopsy should be performed whenever possible.

Detailed information on the stroke (date and time of onset, type, method of detection, outcome) will be collected in the eCRF.

If a stroke occurs after discharge (up to day 30) or after referral to another hospital, the investigator and/or study team ought to use their best efforts to obtain the required information from that hospital.

All strokes will be centrally adjudicated by the Stroke Review Panel (cf. section 8.10).

- Non-intracranial bleeds (total, major, minor, and blood transfusions):

Any reported bleeding, i.e. minor or major bleeds or any bleeding requiring blood transfusion, will be collected in the eCRF to assess the safety of the treatment. Serious bleeds will be reported as serious adverse events as described in section 5.2.1. All bleeds will be recorded in the eCRF. For bleed categories please refer to Appendices.

- Serious cardiac events:

Serious clinical events such as stent thrombosis, reinfarction, CHF, cardiogenic shock will be recorded in the eCRF. For all serious adverse events requiring expedited reporting according to the procedure described in section 5.2.1 a special eSAE form must be completed in addition and must be submitted for further distribution to the Coordinating Center within 24 hours of the investigator becoming aware of the event (see section 8.4.1).

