APPENDIX A: CLINICAL EVENTS TO BE RECORDED IN ECRF

Cardiac events within 30 days

- All-cause mortality
- Cardiac mortality
- Cardiogenic shock
- Congestive heart failure
- Recurrent myocardial infarction
- Stent thrombosis
- Rehospitalisation for cardiac reasons
- Rehospitalisation for non-cardiac reasons

Safety events with 30 days

Total stroke, intracranial haemorrhage, ischaemic stroke, haemorrhagic conversion within 30 days

- Procedure related major bleeds (within 48 hours)
- Non-intracranial bleeds (major, minor) and need for blood transfusions up to 30 days

Evaluations at 1 year

- All-cause mortality

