### **6.3 Safety Secondary Endpoints**

The following observations are considered as endpoints evaluating the safety and will be assessed at 30 days. They are ordered according to medical importance in the indication acute myocardial infarction.

- Total fatal stroke
- Total disabling stroke
- Total non-disabling stroke
- Intracranial haemorrhage

- Ischaemic stroke
- Total stroke (all types)
- Major non-intracranial bleeds (total, with blood transfusion, without blood transfusion)
- blood transfusions
- Minor non-intracranial bleeds
- Total non-intracranial bleeds
- Serious resuscitated ventricular fibrillation
- Serious resuscitated ventricular fibrillation in association during with invasive procedures (occurring at any time during cath /and urgent/elective PCI)

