**Table 11.2 Efficacy secondary endpoints (PPS)**

**Table 12.1 Safety secondary endpoints at day 30 (FAS)**

	PhI (N=#)	P-PCI (N=#)	Relative Risk	P-value	PhI Better	P-PCI Better
Total fatal stroke	n/N (%)	n/N (%)	#	#		
Total disabling stroke	n/N (%)	n/N (%)	#	#		
Total non-disabling stroke	n/N (%)	n/N (%)	#	#		
Intracranial haemorrhage	n/N (%)	n/N (%)	#	#		
Ischaemic stroke	n/N (%)	n/N (%)	#	#		
Total stroke (all types)	n/N (%)	n/N (%)	#	#		
Major non-intracranial bleeds including blood transfusions	n/N (%)	n/N (%)	#	#		
Minor non-intracranial bleeds	n/N (%)	n/N (%)	#	#		
Total non-intracranial bleeds	n/N (%)	n/N (%)	#	#		
Serious resuscitated ventricular fibrillation	n/N (%)	n/N (%)	#	#		
Serious resuscitated ventricular fibrillation in association during with invasive procedures*	n/N (%)	n/N (%)	#	#		

\*: occurring at any time during cath /and urgent/elective PCI

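### Haemorrhagic conversion is a named 30-day safety outcome, but the Stroke Review Panel has no category for it and the SAP no row, so it is never tabulated and is probably missing from the ICH count

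*Protocol*

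**What the plan says.** The safety criteria in the protocol synopsis include "Total stroke, intracranial haemorrhage (ICH), ischaemic stroke, haemorrhagic conversion up to 30 days". Appendix A, which lists the events to be captured in the eCRF, repeats the item: "Total stroke, intracranial haemorrhage, ischaemic stroke, haemorrhagic conversion within 30 days". Both lists keep conversion apart from ICH and from ischaemic stroke. Neither document defines it.

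Protocol 5.2.2 is narrower. Its stroke item reads "Clinically suspected stroke (total (fatal, disabling, non-disabling); ischaemic; intracranial haemorrhage" and does not mention conversion. It does collect "Detailed information on the stroke (date and time of onset, type, method of detection, outcome", requires imaging within 24 hours of a new neurological deficit, and sends all strokes to central adjudication.

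Protocol 8.10 gives the panel the last word: "An independent Stroke Review Panel will perform a final evaluation and classification of documented clinically suspected strokes". The panel works blinded to treatment and is to "assess and classify each stroke event as primary haemorrhagic or ischaemic or unclassifiable".

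SAP 6.3 has six stroke endpoints: fatal, disabling, non-disabling, ICH, ischaemic and total. Table 12.1 has the same six rows, and SAP 9.2 and Table 26.1 repeat them for the pooled elderly sets. None is haemorrhagic conversion.

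**The concern.** Intracranial bleeding is the central safety question of this trial. Protocol 1.1 reports that an excess of ICH in older patients led to the dose reduction in STREAM-1. It also makes the incidence of intracranial and other major bleeding the second main objective. Section 7.2.1 gives ICH particular weight in safety monitoring. A type of intracranial bleed that the protocol itself lists should therefore have a fixed route from adjudication to a results table, and it has none.

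Two things are at stake. First, a listed safety outcome drops out of the report without a recorded decision to drop it. Second, the content of the "Intracranial haemorrhage" row is open. Two analysts could place the same converted infarct in different rows, and could choose after seeing the data. ICH counts are expected to be small, so one or two patients matter to how the contrast reads.

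**Working it through.** The plan states no figure on this point, since the trial has no primary hypothesis or power calculation. The check is mainly a comparison of text.

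**Step 1. Where conversion is named**

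| Place | Stroke categories | Conversion named? |
|---|---|---|
| Protocol synopsis, criteria for safety | total, ICH, ischaemic, conversion | yes |
| Protocol Appendix A | total, ICH, ischaemic, conversion | yes |
| Protocol 5.2.2 | total (by severity), ischaemic, ICH | no |
| Protocol 8.10, Stroke Review Panel | primary haemorrhagic, ischaemic, unclassifiable | no |
| SAP 5 (subclasses for imputation) | ischaemic, ICH, fatal, non-fatal, disabling, non-disabling | no |
| SAP 6.3 and Table 12.1 | fatal, disabling, non-disabling, ICH, ischaemic, total | no |
| SAP 9.2 and Table 26.1 | same six | no |
| SAP History | no entry on conversion | no |

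**Step 2. Following one converted infarct through the plan**

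- It is recorded in the eCRF (Appendix A) and counts in total stroke.
- At the panel, the word primary makes the haemorrhagic category a poor fit for a bleed into an infarct. Ischaemic is the likeliest category, and unclassifiable is possible.
- In the SAP, the ICH row is not defined, is not tied to the panel's primary haemorrhagic category, and is not declared exclusive of the ischaemic row. The SAP also does not say whether its stroke rows use panel or investigator data.
- Apart from blood transfusions, the SAP's other bleeding rows are restricted to non-intracranial bleeds, and Protocol Appendix B1 sets intracranial bleeds aside for separate reporting. If the event is not in the ICH row, no other row shows it as a bleed.

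Three results are therefore possible for the same patient: ischaemic only (likeliest), both ischaemic and ICH, or total stroke only (if unclassifiable, which has no SAP row). None of them shows conversion as such.

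**Step 3. Scale, as illustration only**

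Inputs from Protocol 7.5: 400 pharmaco-invasive (PhI) and 200 primary PCI (PPCI) patients, with STREAM-1 reference ICH rates at age 60 or over of 1.7% and 0%. Assumption: 0, 1 or 2 conversions, all in PhI.

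Expected ICH in PhI: 400 × 0.017 = 6.8, taken as 7. Expected in PPCI: 200 × 0 = 0.

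| Assumed conversions added | PhI count | Rate | Exact 95% CI (Clopper-Pearson) | Change in count | Fisher p against 0/200 |
|---|---|---|---|---|---|
| 0 | 7/400 | 1.75% | 0.71 to 3.57% | none | 0.102 |
| 1 | 8/400 | 2.00% | 0.87 to 3.90% | 8/7, +14% | 0.057 |
| 2 | 9/400 | 2.25% | 1.03 to 4.23% | 9/7, +29% | 0.033 |

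Fisher's test is used here only as an exact check. SAP 8.7 plans a relative risk for these rows. Whatever the base count, one conversion adds 1/400 = 0.25 percentage points in PhI or 1/200 = 0.5 points in PPCI.

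**The case against.** The strongest reply is that the event is not lost. It is recorded in the eCRF with its type, means of detection and outcome, and it counts in total stroke. That stands. A reader might infer that the bleed appears nowhere, but the documents contradict this. What is missing is its adjudication category and its row.

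A reader might also infer that a converted stroke must count only as ischaemic. No passage says so. The SAP's ICH row could admit it, and the panel could call it unclassifiable. Ischaemic is the most natural reading, not a rule. The gap is also not confined to patients given tenecteplase, although its effect would probably fall mostly on PhI.

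Two further inferences are not supported:

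- *That the DSMB would not see conversions.* Protocol 1.4 has the DSMB review all safety data, and 8.10 adds the panel's classification to what it receives. Monitoring detail sits in a charter that is not among these documents.
- *That disability, as in "Total disabling stroke", is graded by unblinded investigators.* The grader and scale are unstated, but Protocol 5.2.2 and 5.5 provide for central adjudication of strokes, and neither document assigns the grading to the site.

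The numerical illustration is also open to challenge, rightly. The 1.7% comes from STREAM-1, where Protocol 1.1 says half-dose was given only to patients aged 75 or over after an amendment. No ICH occurred among the 97 such patients then randomised to the PhI strategy. Seven ICH is therefore not a forecast for this half-dose trial. The number of conversions is assumed, the intervals overlap almost entirely, and every test is exploratory.

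**Conclusion.** The point holds as a gap between a listed outcome and its adjudication and reporting. Haemorrhagic conversion is named twice in the protocol, cannot be recorded as such in the panel's three categories, and has no endpoint or row in the SAP. Followed exactly, the plan never tabulates it and leaves open whether the ICH row includes it. The most likely consequence is that a converted ischaemic stroke is shown as ischaemic and missing from ICH, in either arm.

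This first part rests on the text alone. The likely placement rests on the ordinary reading of the panel's wording. The practical size cannot be derived from the documents. The 7, 8 and 9 event figures show only that a few patients could change how a sparse comparison reads. The gap should be closed because it concerns the trial's main bleeding risk, but it does not undermine the total stroke comparison or the recording of events.

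**What to change.** 1. Define haemorrhagic conversion in the protocol's event definitions or in the SAP.
2. In Protocol 8.10, add a flag to the panel's classification: ischaemic with or without haemorrhagic conversion. The panel assigns it blinded, from imaging already obtained.
3. In SAP 6.3 and Table 12.1, add a descriptive row for conversion and a row for any intracranial bleeding (ICH plus conversion, each patient counted once).
4. State that the stroke rows use panel data and whether the ICH row includes conversions. Keep the ICH row so that it remains comparable with STREAM-1.
5. Add the same rows to SAP 9.2 and Table 26.1 only if STREAM-1 recorded conversions. Neither document shows that it did.

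The cost is one flag on the panel form and two table rows, with no new scans or readers, as the panel already includes a neuroradiologist. The planned trial period ended in June 2022 and the SAP is dated 17 November 2022, so strokes already classified may need a brief blinded re-review. The any-intracranial-bleeding count may also look slightly less favourable than ICH alone.
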